### 10.8.9.3.3. Exploratory Endpoints Analysis

Endpoint	Statistical Analysis Methods
Immunogenicity	
 
For COVID-19 vaccine-naïve participants in this substudy and control group of vaccine-experienced participants from Substudy A,
 
GMTs and 2-sided 95% CIs of SARS-CoV-2 Omi XBB.1.5–neutralizing titers at each time point will be provided for each group, by age subgroup and overall. The statistical methods are described in Section 9.3.1.2.1.
 
GMFRs of SARS-CoV-2 Omi XBB.1.5–neutralizing titers from baseline (before the study vaccination) to each time point after study vaccination, along with the associated 2-sided 95% CIs, will be provided for each group, by age subgroup and overall. Statistical methods are described in Section 9.3.1.2.3.
 
The percentages of participants with seroresponse to SARS-CoV-2 Omicron XBB.1.5 at each time point after vaccination and the associated Clopper-Pearson 95% CIs will be provided for each group, by age subgroup and overall.
 
 
This analysis may be conducted in a selected subset of participants. For control group participants from Substudy A, the above analysis may be performed by baseline SARS-CoV-2 infection status if there is a sufficient number of participants without prior SARS-CoV-2 infection.

COVID-19 cases	
 
Confirmed COVID-19 cases, confirmed severe COVID-19 cases, and strain sequencing of the COVID-19 cases will be summarized.
 

Immune response to emerging variants	For emerging variants (under monitoring, of interest, and/or of concern) not already specified, GMTs, GMFRs, and percentages of participants with seroresponse at the specific time point, along with the associated 95% CIs, will be summarized in the same way as for the exploratory immunogenicity endpoints described above. This analysis may be conducted in a selected subset of participants.
Cell-mediated immune response	The cell-mediated immune response and additional humoral immune response parameters to the Omicron XBB.1.5 strain will be summarized at each time point for the subset of participants with PBMC samples collected in each group.

#### 10.8.9.4. Interim Analyses

No formal interim analysis will be conducted. As this is a sponsor–open-label study, Pfizer may conduct unblinded reviews of the data during the course of the study for the purpose of safety assessment and/or supporting clinical development. Statistical analyses will be carried out when the final data for specified objectives are available while the study is ongoing. The timing of these planned analysis and reporting events is described in Section 10.8.9.4.1.

##### 10.8.9.4.1. Analysis Timing

At a minimum, statistical analyses will be carried out when the following data are available:

- Safety and immunogenicity data through Visit B3 (1 month after study vaccination).
- Safety and immunogenicity data through Visit B5 (6 months after study vaccination).

Additional analyses may be conducted if required for regulatory purposes, to inform product development, and/or for program-level decisions. Certain analyses may be combined as 1 regulatory submission report if the data become available around the same time.

#### 10.8.9.5. Sample Size Determination

This substudy will enroll approximately 300 COVID-19 vaccine–naïve participants. The same number of vaccine-experienced participants will be selected from Substudy A as a control group to evaluate the immunogenicity primary objective. Assuming a 20% nonevaluable rate, approximately 240 evaluable participants in each group will contribute to the evaluation of the immunogenicity primary objective.

For comparisons based on GMR, common assay standard deviations at 1 month after the vaccination in log scale is assumed to be 1.35 based on data observed in Study C4591044. Table 11 provides the power to declare noninferiority under different assumptions of true GMRs of SARS-CoV-2 Omi XBB.1.5–neutralizing titers 1 month after BNT162b2 (Omi XBB.1.5) 30 µg given as a single dose to COVID-19 vaccine–naïve participants in Substudy B to 1 month after BNT162b2 (Omi XBB.1.5) 30 µg given to vaccine-experienced participants in Substudy A, using 1.5-fold margin. If the true GMR is 1.0, the study will have 90.0% power to declare noninferiority. If the true GMR is 0.9, there is 66.6% power to declare noninferiority.

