## 10.7.4. Study Design for Substudy A

### 10.7.4.1. Overall Study Design

This is an open-label Phase 2/3 study to evaluate the safety, tolerability, and immunogenicity of an updated vaccine against COVID-19. Participants 12 through 55 and >55 years of age who have received at least 3 prior doses of a US-authorized mRNA COVID-19 vaccine, with the most recent dose being an Omicron BA.4/BA.5–adapted bivalent vaccine received at least 150 days prior to study vaccination (Visit A1/Day 1), will receive a single open-label 30-µg dose of BNT162b2 (Omi XBB.1.5). Approximately 400 participants will be enrolled. The study duration will be 6 months, with 5 scheduled visits. A reactogenicity e-diary will be used by participants for 7 days from the day of vaccination. The active collection period for AEs will be through approximately 1 month after vaccination and for SAEs through approximately 6 months after vaccination. COVID-19 surveillance will be conducted throughout the study. Blood samples will be taken at each visit for all participants for assessment of immunogenicity. A subset of approximately 30 participants in each age group who consent to collection of optional additional blood samples will comprise the PBMC subset for exploratory evaluation of B- and T-cell responses and HLA typing. See Table 9.

Note: "Enrolled" means a participant's agreement to participate in a clinical study following completion of the informed consent process and randomization or assignment to study intervention.

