##### **10.8.9.1. Statistical Hypotheses**

The immunogenicity primary objective is to assess the noninferiority with respect to level of neutralizing titer and seroresponse rate of the anti-XBB.1.5 immune response induced by BNT162b2 (Omi XBB.1.5) 30 µg given as a single dose to COVID-19 vaccine-naïve participants who were previously exposed to SARS-CoV-2 relative to the immune response elicited by BNT162b2 (Omi XBB.1.5) 30 µg given to vaccine-experienced participants in Substudy A. The primary objective will be evaluated by the following 2 hypotheses:

- The first null hypothesis ( $H_0$ ) is

$$H_0: \ln(\mu_1) - \ln(\mu_2) \leq \ln(0.67) \text{ vs } H_1: \ln(\mu_1) - \ln(\mu_2) > \ln(0.67)$$

where  $\ln(0.67)$  corresponds to a 1.5-fold margin for noninferiority and

- $\ln(\mu_1)$  is the natural log of the geometric mean of SARS-CoV-2 Omi XBB.1.5–neutralizing titers measured at 1 month after BNT162b2 (Omi XBB.1.5) 30 µg given as a single dose to COVID-19 vaccine-naïve participants who were previously exposed to SARS-CoV-2;
- $\ln(\mu_2)$  is the natural log of the geometric mean of SARS-CoV-2 Omi XBB.1.5–neutralizing titers measured at 1 month after BNT162b2 (Omi XBB.1.5) 30 µg given to vaccine-experienced participants in Substudy A.

- The second null hypothesis ( $H_0$ ) is

$$H_0: p_1 - p_2 \leq -0.1 \text{ vs } H_1: p_1 - p_2 > -0.1$$

where -10% is the noninferiority margin for seroresponse and

- $p_1$  is the percentage of participants with seroresponse to the Omi XBB.1.5 strain at 1 month after BNT162b2 (Omi XBB.1.5) 30 µg given as a single dose to COVID-19 vaccine-naïve participants who were previously exposed to SARS-CoV-2;
- $p_2$  is the percentage of participants with seroresponse to the Omi XBB.1.5 strain at 1 month after BNT162b2 (Omi XBB.1.5) 30 µg given to vaccine-experienced participants in Substudy A.

Seroresponse is defined as achieving a  $\geq 4$ -fold rise from baseline (before the study vaccination). If the baseline measurement is below the LLOQ, the postvaccination measure of  $\geq 4 \times \text{LLOQ}$  is considered seroresponse.

Noninferiority based on GMR will be declared if the lower limit of the 2-sided 95% CI for the GMR is greater than 0.67; noninferiority based on seroresponse will be declared if the lower limit of the 2-sided 95% CI for the difference in percentages of participants with seroresponse is greater than -10%.

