#### 10.8.9.1.2. Multiplicity Adjustment

The 2 hypotheses for the primary objective will be evaluated sequentially using a 1-sided alpha of 0.025. Noninferiority based on GMR will be evaluated first, followed by seroresponse rate difference.

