Substudy B is an open-label Phase 2/3 study to evaluate the safety, tolerability, and immunogenicity of an updated vaccine against COVID-19, targeting the XBB.1.5 strain. Participants ≥ 12 years of age who were previously exposed to SARS-CoV-2 and are COVID-19 vaccine-naïve will receive a single 30- μ g dose of BNT162b2 (Omi XBB.1.5). Approximately 300 participants will be enrolled (see Table 5 and Figure 2). The study duration will be 6 months, with 5 scheduled visits. A reactogenicity e-diary will be used by participants for 7 days from the day of vaccination. The active collection period for AEs will be through approximately 1 month after vaccination and for SAEs through approximately 6 months after vaccination. COVID-19 surveillance will be conducted throughout the study. Blood samples will be taken at each visit for all participants for assessment of immunogenicity. A subset of approximately 30 participants ≥ 18 years of age who consent to optional additional blood samples will comprise the PBMC subset for exploratory evaluation of B- and T-cell responses and HLA typing.

Table 5. Substudy B Design

Vaccine: BNT162b2 (Omi XBB.1.5)						
Group	Participant Age Group	Prior Doses	Time Since Last Dose	Study Dose	Number of Participants	Randomization/Blind
1	≥12 Years	0		30 µg	300	Open-label

Participants from the C4591054 Substudy A study who received the BNT162b2 (Omi XBB.1.5) 30 µg as a booster dose will be used as a control group to assess the immunogenicity objectives.

An EDMC will review all safety data throughout the study.

Figure 2. Schema of Substudy B

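### Substudy B selects about 300 of about 400 Substudy A participants as controls, with no selection rule; using all evaluable controls would gain power without adding any planned assay

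*Protocol*

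**What the plan says.** Protocol Section 10.8.9.5 (Sample Size Determination, Substudy B) sets Substudy B at approximately 300 and continues: "The same number of vaccine-experienced participants will be selected from Substudy A as a control group to evaluate the immunogenicity primary objective". With 20% nonevaluable, that gives 240 per group, the basis of Tables 11 and 12.

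For Substudy A, Section 10.7.4.1 says: "Approximately 400 participants will be enrolled". Table 9 splits these into 200 aged 12-55 and 200 aged over 55.

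Elsewhere no selection step appears. The synopsis and Section 10.8.4.1 (under Table 10) name the Substudy A recipients as the control group. SAP Section 2.3 for Substudies A and B does the same, saying that those who received the vaccine "as a booster dose will be used as a control group to assess the immunogenicity objectives". SAP Sections 4 and 6.1.2.2 define the analysis set only as the evaluable immunogenicity population, and SAP Section 2.1 declares no modification of the protocol's analysis plan.

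On testing, Section 10.8.9.1.2 says: "The 2 hypotheses for the primary objective will be evaluated sequentially using a 1-sided alpha of 0.025", with the GMR first and seroresponse second.

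**The concern.** Section 10.8.9.5 names a number and stops there. It does not mention a random draw, matching, an age quota, order of enrolment, the time of selection or who is responsible for it. No reason is given for equal group sizes.

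The excluded controls cost nothing extra to measure. Substudy A's primary immunogenicity estimands are GMT, fold rise and seroresponse for XBB.1.5 at 1 month (Section 10.7.3; SAP Section 6.1.2.1), which need both baseline and 1-month titers. The footnote that allows testing in a subset is attached only to exploratory objectives.

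Two things are at stake. The first is precision in the only confirmatory comparison in this protocol, above all for seroresponse, the weaker of the two tests. The second is an open choice of comparator. The substudy is open-label, most sponsor staff are unblinded (Section 10.8.6.4.3), and unblinded data reviews are permitted (Section 10.8.9.4).

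**Working it through.** **Inputs.** From Section 10.8.9.5: the SD "in log scale is assumed to be 1.35 based on data observed in Study C4591044"; 20% nonevaluable; 240 per group. From Section 10.8.9.1: GMR margin 0.67 and seroresponse margin -10 percentage points. One-sided alpha is 0.025.

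**Evaluable controls.** Selected: 300 × 0.8 = 240. All: 400 × 0.8 = 320. Left out: 100 of 400 (25%), or 80 evaluable.

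**GMR.** SE = 1.35 × √(1/n_B + 1/n_A). The noncentrality is (ln GMR − ln 0.67)/SE, and power comes from the noncentral t distribution with n_B + n_A − 2 degrees of freedom.

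- 240/240: SE = 0.1232. At GMR 1.0 the noncentrality is 0.4005/0.1232 = 3.25.
- 240/320: SE = 0.1153. At GMR 1.0 the noncentrality is 0.4005/0.1153 = 3.47.
- Ratio of standard errors: √[(1/240 + 1/320)/(2/240)] = 0.935, a 6.5% reduction. The equivalent equal group size is 2/(1/240 + 1/320) = 274.

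| True GMR | Table 11 | Reproduced, 240/240 | 240/320 |
|---|---|---|---|
| 1.0 | 90.0 | 90.0 | 93.4 |
| 0.9 | 66.6 | 66.6 | 72.4 |
| 0.8 | 30.0 | 30.0 | 33.6 |

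**Seroresponse.** The Farrington-Manning score test was used: power = Φ[(p_B − p_A + 0.10 − 1.96 × SE0)/SE1]. SE0 uses the proportions fitted under a difference of -0.10, and SE1 uses the assumed true proportions. At 80/80:

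- 240/240: SE0 = 0.0368, SE1 = 0.0365, power 77.7%.
- 240/320: SE0 = 0.0353, SE1 = 0.0342, power 81.7%.

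| Rate in A / rate in B | Table 12 | Reproduced, 240/240 | 240/320 |
|---|---|---|---|
| 80 / 80 | 77.7 | 77.7 | 81.7 |
| 80 / 75 | 25.9 | 25.9 | 27.9 |
| 70 / 70 | 66.8 | 66.8 | 71.7 |
| 70 / 65 | 21.7 | 21.7 | 23.7 |
| 60 / 60 | 61.2 | 61.2 | 66.6 |
| 60 / 55 | 19.9 | 19.9 | 22.0 |

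**Both hypotheses together.** This depends on the correlation between the two tests, which the documents do not give, so only a range is possible. At GMR 1.0 and 80/80, independence gives 0.900 × 0.777 = 70% now and 0.934 × 0.817 = 76% with all controls. Full overlap gives the smaller of the two powers, 78% now and 82% with all controls.

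**The case against.** **Equal groups with 90.0% GMR power are a legitimate design, and a subset might help comparability.** Substudy A is split 200/200 by age, whereas Substudy B has no age quota. Section 2.2.1 reports generally higher postvaccination titers over age 55, so a draw matched on age could have a purpose. The documents state no such purpose and no such draw, and both primary analyses already account for age and baseline titer. The gain of 3.4 points at GMR 1.0 is modest. That stands.

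**Safeguards exist.** Serology staff are blinded to intervention, identity, visit and cohort. SAP Section 4 has membership of analysis populations decided and documented before database release. The primary model adjusts for baseline titer and age, and the seroresponse analysis stratifies on both. These limit the possible bias, but they do not supply a selection rule or cover selection on other characteristics.

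**The result is known.** Section 2.2.1 of this amendment reports that Substudy B demonstrated noninferiority. Added power cannot alter that test, and redefining its comparator now would itself be a choice made after the data were seen. This stands in full and shapes the fix.

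Three stronger readings might be inferred, and the documents do not support them:

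- *The excluded controls had already been assayed, or titers were known when the 300 were chosen.* The assays are planned for all evaluable participants, but nothing says they come before selection. Section 10.8.4.3 calls Substudy A a contemporaneous comparator.
- *The protocol and the SAP conflict.* The protocol's synopsis and Section 10.8.4.1 use essentially the SAP's description. Section 10.8.9.5 is the outlier, and the other places can be read as naming the source population.
- *The sample size was miscalculated.* Tables 11 and 12 reproduce.

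**Conclusion.** The point holds as a gap in efficiency and prespecification. About 300 controls are taken from about 400 by an unstated method, and about 80 evaluable controls whose titers are planned anyway are left out. Using them would add 3.4 to 5.8 percentage points to GMR power across Table 11 and about 2 to 5.4 points to seroresponse power across Table 12.

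This rests on three assumptions: the 20% nonevaluable rate applies to all of Substudy A; the SD of 1.35 is common to both groups; and the assumed seroresponse rates are those of Table 12. The size of any bias from the open choice cannot be derived from the documents. Nothing here shows that the reported noninferiority finding is wrong.

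**What to change.** 1. In Protocol Section 10.8.9.5, define the control as all evaluable Substudy A participants (approximately 320). Put the same definition in SAP Section 6.1.2.2, and align the synopsis, Section 10.8.4.1 and SAP Section 2.3 with it.
2. Recompute Tables 11 and 12 for 240 against about 320.
3. For the completed noninferiority test, keep the comparator that was used. State how, when and by whom the 300 were selected. Report the analysis with all evaluable controls as a sensitivity analysis, labelled as added after the result was known.
4. Use the all-evaluable definition for the remaining control comparisons, such as the exploratory ones through 6 months in Section 10.8.9.3.3 and SAP Section 6.2.1.2.

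The cost is wording, two recomputed tables, one extra analysis and unequal group sizes, which the planned methods accommodate. No new participants, samples or planned assays are needed.

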**Table 11. Power to Demonstrate Noninferiority Under Different Assumptions of GMR**

Number of Evaluable Participants in Each Group	Assumed True GMR	Power
240	1.0	90.0
240	0.9	66.6
240	0.8	30.0

Table 12 provides the power to demonstrate noninferiority under different assumptions of seroresponse rates for each comparative group, using a 10% margin. If the seroresponse rate is 80% in both comparator groups, the study will have 77.7% power to demonstrate noninferiority. If the seroresponse rate is 80% for vaccine-experienced participants in the Substudy A control group and 75% for vaccine-naïve participants in Substudy B, the study will have 25.9% power to demonstrate noninferiority.

**Table 12. Power to Demonstrate Noninferiority Under Different Assumptions of Seroresponse Rate**

Number of Evaluable Participants in Each Group	Assumed Seroresponse Rate in Substudy A Control Group (%)	Assumed Seroresponse Rate in Substudy B (%)	Power
240	80	80	77.7
240	80	75	25.9
240	70	70	66.8
240	70	65	21.7
240	60	60	61.2
240	60	55	19.9

[figure not shown]
## 10.9. Appendix 9: Substudy C

[figure not shown]
### 10.9.1. Substudy C Summary

#### 10.9.1.1. Synopsis

[figure not shown]
See [Section 1.1](#) for the synopsis of Substudy C.

#### 10.9.1.2. Schemas

- a. A maximum of 20 participants 12 through 17 years of age will be enrolled. If fewer than 20 participants are enrolled in this age group, the difference will be added to the number of participants enrolled in the 18-through 55-year age group.

### 10.9.1.3. Schedule of Activities for Substudy C

Visit Identifier	C1	C2	C3	C4	C5	C6	Unplanned	Notes
Visit Description	Vax 1 Visit	1-Week Follow-Up Visit (Vax 1)	2-Week Follow-Up Visit (Vax 1)	1-Month Follow-Up Visit (Vax 1)	3-Month Follow-Up Visit (Vax 1)	6-Month Follow-Up Visit (Vax 1)	Potential COVID-19 Illness Visit	The COVID-19 illness visit may be conducted as an in-person or telehealth visit. The COVID-19 illness visit is only conducted for symptomatic participants. See Section 10.9.8.5.9 .
Visit Window	Day 1	6 to 8 Days After Visit C1	12 to 16 Days After Visit C1	28 to 35 Days After Visit C1	84 to 98 Days After Visit C1	175 to 189 Days After Visit C1	Optimally Within 3 Days After Potential COVID-19 Illness Onset	3-Month and 6-month visits may be performed as telehealth visits if the participant had blood draws discontinued.
			ONLY FOR COHORTS 1 and 3					
Obtain informed consent/assent	X							If vaccination is temporarily delayed, per Section 10.9.5.5 , consent need not be obtained again on the day of vaccination.  For participants <18 years of age (at the time of consent), the parent(s)/legal guardian will provide signed informed consent. Depending on the age of the participant and according to local requirements, participants will also be asked to provide assent as appropriate (verbal or written).
Assign participant number	X							If the participant is from a prior Pfizer COVID-19 study(ies), record the participant number(s) of the prior study(ies) in the CRF.
Obtain demography data	X							
Obtain authorization for and perform the participant verification process via third-party vendor, if applicable	X							Refer to Section 10.9.8.5.1 for details.

Visit Identifier	C1	C2	C3	C4	C5	C6	Unplanned	Notes
Visit Description	Vax 1 Visit	1-Week Follow-Up Visit (Vax 1)	2-Week Follow-Up Visit (Vax 1)	1-Month Follow-Up Visit (Vax 1)	3-Month Follow-Up Visit (Vax 1)	6-Month Follow-Up Visit (Vax 1)	Potential COVID-19 Illness Visit	The COVID-19 illness visit may be conducted as an in-person or telehealth visit. The COVID-19 illness visit is only conducted for symptomatic participants. See Section 10.9.8.5.9 .
Visit Window	Day 1	6 to 8 Days After Visit C1	12 to 16 Days After Visit C1	28 to 35 Days After Visit C1	84 to 98 Days After Visit C1	175 to 189 Days After Visit C1	Optimally Within 3 Days After Potential COVID-19 Illness Onset	3-Month and 6-month visits may be performed as telehealth visits if the participant had blood draws discontinued.
			ONLY FOR COHORTS 1 and 3					
Obtain medical history data (including confirmed COVID-19 diagnosis or asymptomatic positive SARS-CoV-2 test result)	X							
Record details of all prior COVID-19 vaccines (if applicable)	X							Record details in the prior COVID-19 vaccination CRF.
Urine pregnancy test (if appropriate)	X							Refer to Section 8.3.6 .
Confirm use of contraceptives (if appropriate)	X	X	X	X				Refer to Section 5.3.1 .
Measure height and weight	X							
Perform clinical assessment	X	X	X	X				Including, if indicated, a physical examination ( Section 10.9.8.3.1 ).
Record nonstudy vaccine information	X	X	X	X	X	X	X	Refer to Section 10.9.6.9 .
Record prohibited medication use		X	X	X	X	X	X	Refer to Section 10.9.6.9.1 .
Confirm eligibility	X							Refer to Section 10.9.5.1 and Section 10.9.5.2 .
Measure body temperature	X							
Review temporary delay criteria	X							See Section 10.9.5.5 .
Obtain randomization number using the IRT system	X							Refer to Section 10.9.8.5.1 .
Nasal (midturbinate) swab for SARS-CoV-2 NAAT	X						X	

Visit Identifier	C1	C2	C3	C4	C5	C6	Unplanned	Notes
Visit Description	Vax 1 Visit	1-Week Follow-Up Visit (Vax 1)	2-Week Follow-Up Visit (Vax 1)	1-Month Follow-Up Visit (Vax 1)	3-Month Follow-Up Visit (Vax 1)	6-Month Follow-Up Visit (Vax 1)	Potential COVID-19 Illness Visit	The COVID-19 illness visit may be conducted as an in-person or telehealth visit. The COVID-19 illness visit is only conducted for symptomatic participants. See Section 10.9.8.5.9 .
Visit Window	Day 1	6 to 8 Days After Visit C1	12 to 16 Days After Visit C1	28 to 35 Days After Visit C1	84 to 98 Days After Visit C1	175 to 189 Days After Visit C1	Optimally Within 3 Days After Potential COVID-19 Illness Onset	3-Month and 6-month visits may be performed as telehealth visits if the participant had blood draws discontinued.
			ONLY FOR COHORTS 1 and 3					
Blood sample for immunogenicity assessments	~50 mL / ~10 mL*	~20 mL / ~10 mL*	~20 mL	~50 mL / ~10 mL*	~20 mL / ~10 mL*	~20 mL / ~10 mL*		≥18-Year-olds: 50 mL/20 mL is to be collected. * 12-17-Year-olds: 10 mL is to be collected (Cohort 2 only).  Blood sample collection may be halted or discontinued upon notification by Pfizer.
Blood sample for PBMC isolation – Cohort 2 and Cohort 3	~130 mL	~130 mL		~130 mL		~130 mL		Applicable at designated Cohort 2 and Cohort 3 sites only. Optional with additional consent given by participants ≥18 years of age. See Section 10.9.8.2.2 .
Blood sample for HLA typing – Cohort 2 and Cohort 3	~5 mL							Applicable at designated Cohort 2 and Cohort 3 sites only. Optional with additional consent given by participants ≥18 years of age. See Section 10.9.8.2.2 .
“Unblinded” staff obtains the participant’s vaccine vial allocation using the IRT system	X							Refer to Section 10.9.8.5.1 .
“Unblinded” staff administers study intervention	X							Refer to Section 6.1.1 .

Visit Identifier	C1	C2	C3	C4	C5	C6	Unplanned	Notes
Visit Description	Vax 1 Visit	1-Week Follow-Up Visit (Vax 1)	2-Week Follow-Up Visit (Vax 1)	1-Month Follow-Up Visit (Vax 1)	3-Month Follow-Up Visit (Vax 1)	6-Month Follow-Up Visit (Vax 1)	Potential COVID-19 Illness Visit	The COVID-19 illness visit may be conducted as an in-person or telehealth visit. The COVID-19 illness visit is only conducted for symptomatic participants. See Section 10.9.8.5.9 .
Visit Window	Day 1	6 to 8 Days After Visit C1	12 to 16 Days After Visit C1	28 to 35 Days After Visit C1	84 to 98 Days After Visit C1	175 to 189 Days After Visit C1	Optimally Within 3 Days After Potential COVID-19 Illness Onset	3-Month and 6-month visits may be performed as telehealth visits if the participant had blood draws discontinued.
			ONLY FOR COHORTS 1 and 3					
Assess acute reactions (immediate events) for at least 30 minutes after study intervention administration	X							
Explain participant communication methods (including for potential COVID-19 illness and reactogenicity e-diary completion and severe reactogenicity symptoms), assist the participant with downloading the app or issue provisioned device, if required	X							
Provide thermometer and measuring device	X							
Provide/ensure participant has a self-swab kit in case of COVID-19 symptoms and instructions on self-collection of nasal swabs	X	X	X	X	X			
Ask/remind the participant to contact the site if the participant experiences any severe (Grade 3) reactogenicity symptoms	X	X						
Ask/remind the participant to contact the site if a medically attended event or hospitalization occurs	X	X	X	X	X			

Visit Identifier	C1	C2	C3	C4	C5	C6	Unplanned	Notes
Visit Description	Vax 1 Visit	1-Week Follow-Up Visit (Vax 1)	2-Week Follow-Up Visit (Vax 1)	1-Month Follow-Up Visit (Vax 1)	3-Month Follow-Up Visit (Vax 1)	6-Month Follow-Up Visit (Vax 1)	Potential COVID-19 Illness Visit	The COVID-19 illness visit may be conducted as an in-person or telehealth visit. The COVID-19 illness visit is only conducted for symptomatic participants. See Section 10.9.8.5.9 .
Visit Window	Day 1	6 to 8 Days After Visit C1	12 to 16 Days After Visit C1	28 to 35 Days After Visit C1	84 to 98 Days After Visit C1	175 to 189 Days After Visit C1	Optimally Within 3 Days After Potential COVID-19 Illness Onset	3-Month and 6-month visits may be performed as telehealth visits if the participant had blood draws discontinued.
			ONLY FOR COHORTS 1 and 3					
Ask/remind the participant to contact the site immediately if the participant experiences any symptoms as detailed in Section 10.9.8.5.8 (COVID-19 or MIS-C)	X	X	X	X	X			
Participant completes COVID-19 illness e-diary		←					→	Refer to Section 10.9.8.3.4 and Section 10.9.8.5.8 .
Ask/remind the participant to contact the site immediately if the participant experiences any symptoms of acute chest pain, shortness of breath, or palpitations	X	X	X	X				Report the specified cardiac illness symptoms through 42 days after study vaccination. Refer to Section 10.9.8.5.11 .
Review of e-diary data with participant follow-up until ongoing symptom resolution	←			→				Daily review is optimal during the active diary period. E-diary data reviewed at Visits C2, C3 (Cohorts 1 and 3 only), and C4 with participant follow-up until ongoing symptom resolution (obtain stop dates). Assess compliance, record any medically attended events (including hospitalizations), and collect stop dates for any symptoms ongoing on the last day of the e-diary collection period (7 days) in the CRF.

Visit Identifier	C1	C2	C3	C4	C5	C6	Unplanned	Notes
Visit Description	Vax 1 Visit	1-Week Follow-Up Visit (Vax 1)	2-Week Follow-Up Visit (Vax 1)	1-Month Follow-Up Visit (Vax 1)	3-Month Follow-Up Visit (Vax 1)	6-Month Follow-Up Visit (Vax 1)	Potential COVID-19 Illness Visit	The COVID-19 illness visit may be conducted as an in-person or telehealth visit. The COVID-19 illness visit is only conducted for symptomatic participants. See Section 10.9.8.5.9 .
Visit Window	Day 1	6 to 8 Days After Visit C1	12 to 16 Days After Visit C1	28 to 35 Days After Visit C1	84 to 98 Days After Visit C1	175 to 189 Days After Visit C1	Optimally Within 3 Days After Potential COVID-19 Illness Onset	3-Month and 6-month visits may be performed as telehealth visits if the participant had blood draws discontinued.
			ONLY FOR COHORTS 1 and 3					
Collect AEs and SAEs as appropriate	X	X	X	X	X	X	X	Includes nonserious AEs through Visit C4; any AEs occurring up to 48 hours after a blood draw or nasal swab collection; and SAEs or potential menstrual cycle disturbances through the end of the study (see Section 8.4.1 and Section 10.9.8.4.1 ).
Collection of COVID-19/MIS-C–related clinical and laboratory information (including local diagnosis)							X	Refer to Section 10.9.8.2.1 .
Assist the participant to delete the e-diary application or collect the provisioned device						X		

